### Specific Aims/Hypotheses

**Aim 1:** To establish efficacy, safety and acceptability of the MACRO intervention via a RCT.

We hypothesize that after 3 months, compared to standard of care (SOC), participants randomized into the MACRO arm will have:

H1.1: Greater improvements in function as measured by Activity Measure for Post-Acute Care Computer Adaptive Test (AM-PAC-CAT) Basic Mobility Domain (primary outcome).

H1.2: Greater improvements in function as measured by accelerometry; AM-PAC CAT Daily Activity Domain; depression; frailty; self-efficacy; and quality of life. These will be collected to the extent possible in respect to local limitations that may result from fluctuations in COVID-19 prevalence.

H1.3: Greater CR participation and adherence.

H1.4: Greater impact in readmissions and hospitalization.

**Aim 2:** To examine the duration of benefit of MACRO compared to SOC.

H2.1: We hypothesize that relative MACRO benefits (i.e., function indices (see H1.2), adherence and readmissions/hospitalization will persist after 6 and 12 months (12 months will be captured as timing allows)

**Aim 3:** To explore characteristics of patients who benefit the most from the MACRO intervention.

H3.1: We anticipate functional capacity and other baseline characteristics will identify those who benefit from the MACRO intervention (exploratory).

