##### **B. Randomization**

We will use the high quality pseudo-random deviate generator in SAS® (SAS Institute, Inc., Cary, North Carolina) to randomize participants to MACRO or SOC in 1:1 ratio with random block sizes chosen from small even numbers. Exact block sizes will be revealed to the rest of the study team at the conclusion of the study to prevent educated guessing. There are some key demographic differences in populations served by the study sites, as described in the Study Settings section. Thus, randomization will be stratified by site to ensure a balance between the treatment groups with respect to site by design rather than chance. To retain maximum degree of flexibility in post-COVID-19 environment, no other stratification criterion will be employed. The statistician will create schedules which link the randomization sequence number and treatment arm and will provide them to the team constructing the data management system. At randomization, a study team member will establish the link between the participant study identifier and randomization sequence number by clicking on a database function. Randomization data will only be visible to the study statistician and intervention delivery personnel. Therefore, all personnel involved in post assessments will be blind to treatment assignment.

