## 7.0 Procedures Involved

### 7.1 Study design.

**Overview and summary of design:** This is a pragmatic randomized controlled trial (RCT) of 374 older adults, with 40 subjects at the University of Pittsburgh, eligible for CR: hospitalized adults aged  $\geq 70$  years with a primary diagnosis of AMI/ACS, stable IHD, CABG, PCI, valvular heart disease (valve replacements or repairs for aortic stenosis or mitral regurgitation), PAD or HF. Patients who consent to participate will be randomly assigned to MACRO or SOC arms (which may include CR at the discretion of the providers) (Figure below). In the MACRO arm, patients will benefit from personalized engagement and CR will be explicitly facilitated, enhanced, tailored to patients' preferences and needs, and utilizing a flexible range of options (site-, home, or hybrid). In comparison, SOC provides no specialized engagement, and no programmatic facilitation, enhancement, customization, or deliberate flexibility in how care is provided.

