- K. **Physical activity.** Physical activity will be measured in all participants at each assessment for approximately 7-10 days using the ActiGraph accelerometer. Participants are asked to wear the ActiGraph on their wrist for 7-10 days, removing it only for times when the arm will be submerged in water for long periods of time like swimming. After 7-10 days, participants will mail the accelerometer back to the study team in a stamped, pre-addressed envelope provided to them at their study visit, or they will bring it with them to their next scheduled visit. We may also contact participants by telephone to ensure monitors are returned.
- L. **Adherence to the cardiac rehabilitation program.** An assessment of the total number of CR sessions participants complete will be tracked via telephone calls, collection of data from the onsite cardiac rehabilitation programs, and/or self-report by participants at the completion of the study.
- M. **Risk Assessment.** The aggregate risk of each participant will be assessed at baseline. We will assess risk across three domains: medical, functional, and psychosocial. An assignment of high, moderate, or low risk will be determined using the participants’ scores on various baseline assessments.

- N. **Duke Activity Status Index (DASI)** is a 12-item scale that has been validated in cardiac patients against peak VO2 and has been demonstrated to be a reliable and responsive tool to quantify physical activity in daily living.
- O. **FRAIL Scale.** A five-item scale frailty assessment that assesses Fatigue, Resistance, Ambulation, Illnesses, and Loss of weight that can be administered over the phone.
- P. **Rapid Estimate of Adult Literacy (REALM-SF).** (optional as now contingent on COVID-19 risk) Will be utilized to evaluate health literacy on all participants.
- Q. **Nutrition:** Will be assessed with the Rapid Eating Assessment for Participants short (REAP-S) (to be collected at all sites) and a 3-day food record (not collected at WU site). REAP-S is a 16-item questionnaire to assess eating habits for patients. A 3-day food record allows will also be collected to assess quantities of specific food groups (such as protein).

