## MACRO Intervention

**Early Contact.** MACRO study staff will continue to monitor inpatient participants electronic medical record charts for consults to PT/OT/CR. Education will be provided over the phone or in person to enhance the transition to home and to facilitate transition to outpatient CR. The rationale for CR will be explained and the shared decision making between the patient and providers will be emphasized.

**Risk Determination.** Aggregate risk assessment will be completed on each participant (both MACRO intervention and controls) with methods that integrate baseline study indices across three domains: medical, functional, and psychosocial. In the MACRO Intervention group only, these risk assessment scores will be used as a means to inform coaches of broad patient challenges that need to be addressed with CR care, as parts of site-, hybrid- and home-based options.

**MACRO Intervention arm transitional care:** The MACRO Intervention includes therapeutic reinforcements in the days after discharge/enrollment. When feasible, home calls start the week of discharge/enrollment, study staff will contact the participant approximately once each week (intent to treat) to address questions and to encourage the patient to continue the chosen CR option (site-, home-, or hybrid). Phone calls will continue throughout the phase II CR period to help ensure adherence and as recovery evolves.

Our methods for maintaining care and observation throughout transitions (including to skilled term nursing facility [SNFs] or rehab) were developed at the VAPHS and include (1) Establishing rapport with potential participants and their families; (2) Collecting information for several different methods of contact to ensure close communication over the duration of the study; (3) Phone calls with participants intermittently while they are at SNF or inpatient rehab; (4) sending reminders to the participants and their family members that the team will be calling them; (5) Verification of discharge plan at SNF/rehab discharge and confirmation that alternate contact information is up-to-date.

**Patients in the MACRO Intervention arm will be encouraged to participate in outpatient phase 2 Clinical CR (site-, home- or hybrid-based options)**

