**MACRO Intervention arm telephone intervention.** MACRO staff will contact participants randomized to the MACRO arm approximately once each week until the completion of phase II after which approximately monthly phone calls will be completed. A subset of telephone calls will have a second MACRO staff member listening to calls to enable additional monitoring. The components of each session recorded on the checklist.

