### **7.3 Quality Assurance**

- A. **Fidelity** refers to whether team members consistently perform the MACRO intervention with a high level of adherence to and competence with the intervention protocol. Low fidelity is a common and often unrecognized problem leading to “failed” intervention studies. We will apply expertise from numerous intervention studies, including multi-site studies: (1) Attaining fidelity – we will train team members at each site. (2) Measuring and maintaining fidelity – Co-investigators will have regular supervisory calls with team members. Their intervention sessions may be randomly sampled by the supervisors and rated according to meeting fidelity standards. The PIs are the ultimate fidelity supervisors; they will be in regular contact with the supervisors, study coordinators, and research assistants to promptly detect and correct problems. Such training and monitoring have been successful in our recent rehabilitation studies.
- B. **Interventionist training and certification.** Prior to beginning the study, the research staff will be trained on the intervention. Regular telephone calls will be held with intervention research staff to discuss problem participants or challenging issues that arise in the delivery of the intervention.
- C. **SOC control group.** The SOC group controls for the possibility that regular contact with the study team may improve outcomes in participants randomized to the intervention. Participants randomized to the SOC group will follow the standard hospital process and may or may not receive CR.
- D. **Quality control of outcome measures.** All research study staff will be trained in each aspect of the study that they are involved in. Training will be completed by subject matter experts in the specific area within the research team. Data will be reviewed for quality control, standardization, and abnormalities in collection and will be discussed at regular meetings.

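### The CR session count behind H1.3 may come from different sources in the two arms, because only MACRO participants receive recurring study calls

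*Combined protocol and SAP*

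**What the plan says.** The hypothesis is "H1.3: Greater CR participation and adherence" (section 1.1). The measure is in section 7.2, item L: the total of completed CR sessions "will be tracked via telephone calls, collection of data from the onsite cardiac rehabilitation programs, and/or self-report by participants", with study end given as the time point. No source is ranked first, none is required in both arms, and no rule settles disagreement between sources.

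On contact with participants:

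- **MACRO.** "MACRO staff will contact participants randomized to the MACRO arm approximately once each week until the completion of phase II", then about monthly (section 7.2, telephone intervention). The calls have a therapeutic aim: "Phone calls will continue throughout the phase II CR period to help ensure adherence and as recovery evolves" (section 7.2, transitional care).
- **SOC.** "SOC provides no specialized engagement, and no programmatic facilitation, enhancement, customization, or deliberate flexibility in how care is provided" (section 7.1), and "Participants randomized to the SOC group will follow the standard hospital process and may or may not receive CR" (section 7.3, item C). The same item says "The SOC group controls for the possibility that regular contact with the study team may improve outcomes", but no matching contact schedule for SOC is given.
- **Blinding.** "Randomization data will only be visible to the study statistician and intervention delivery personnel" (section 3.1 B). MACRO callers therefore know the allocation; outcome assessors do not.

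The Aim 1 analysis (section 9.1 C) compares participation and adherence between arms with Wilcoxon, chi-square or Fisher tests.

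**The concern.** A between-arm comparison is fair only if the outcome is ascertained in the same way in both arms. Item L permits a MACRO session to be logged during a coaching call soon after it happens, by an unblinded caller whose task is to encourage attendance. No equivalent route is described for SOC. Part of any recorded difference in H1.3 could then reflect how sessions were counted rather than how many took place.

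This matters because low participation is the problem MACRO was built to address (section 1.1), so H1.3 will be read closely even as a secondary hypothesis.

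**Working it through.** **1. Is there a figure to reproduce?** The plan gives no expected value, capture rate or power for adherence. Its only calculation is for the primary outcome (section 9.1 D), and it reproduces: 2.60 points, SD 7.97, two-sided 0.05 and 149 per arm give 80.4% power by the normal approximation, and 149/0.80 = 186.25, rounded up to 187 per arm. Here it supplies only n = 149 per arm.

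**2. Which calls could feed the count?** Item L lists telephone calls separately from self-report.

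| Contact described | MACRO | SOC |
|---|---|---|
| Assessments at 3, 6 and 12 months, possibly by telephone | yes | yes |
| Possible call about returning the activity monitor | yes | yes |
| Roughly weekly coaching calls in phase II, then monthly | yes | no |

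The text permits coaching calls as a source; it does not say they will be used.

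**3. Does anything downstream correct unequal measurement?** Section 9.1 C provides for intention-to-treat analysis, multiple imputation, covariate adjustment in sensitivity analyses, zero-inflated models, dichotomized outcomes and transformations. None concerns the source of the count.

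**4. Timing.** Item L refers to study end, Table 1 schedules adherence at 3, 6 and 12 months, and the Aim 1 analysis treats it as a single 3-month measurement. H2.1 also expects the adherence benefit to persist at 6 and 12 months, which a single 3-month measurement cannot show.

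**5. Hypothetical size for session counts.** All capture rates are assumptions. Recorded mean = true mean × capture. With 12 true sessions in both arms:

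- MACRO at 95%: 12 × 0.95 = 11.4.
- SOC at 75%: 12 × 0.75 = 9.0. The difference is 2.4 and the ratio 11.4/9.0 = 1.27.
- SOC at 85% or 65%: ratios 0.95/0.85 = 1.12 and 0.95/0.65 = 1.46.

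The ratio is simply MACRO capture over SOC capture. If SOC self-report overstated attendance, it would fall below 1.

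**6. Hypothetical effect on the test of participation (yes/no).** Let true participation be p in both arms, with recorded proportions a = p·c_M and b = p·c_S, d = a − b, and m = (a + b)/2. Then SE0 = √[2m(1 − m)/n], SE1 = √{[a(1 − a) + b(1 − b)]/n}, and the rejection rate is Φ[(d − 1.96·SE0)/SE1] + Φ[(−d − 1.96·SE0)/SE1].

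With p = 0.50, c_M = 0.95 and n = 149:

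| SOC capture | Recorded, MACRO vs SOC | False-positive rate |
|---|---|---|
| 90% | 47.5% vs 45.0% | 7% |
| 85% | 47.5% vs 42.5% | 14% |
| 80% | 47.5% vs 40.0% | 26% |
| 70% | 47.5% vs 35.0% | 59% |

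For the 80% row, m = 0.4375, SE0 = 0.0575 and SE1 = 0.0573; (0.075 − 0.1127)/0.0573 = −0.66, which gives 26%. At 95% vs 80% capture, letting p run from 13% to 64% (the participation figures in section 1.1) gives 8% to 39%. Equal capture (90% in both arms) gives 5%.

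**7. The same for a Wilcoxon test on counts.** A simulation (3000 runs, 149 per arm) assumed that half attend, with 1 to 36 sessions each. At 95% vs 80% capture, mean recorded sessions were 8.8 vs 7.4 and the test rejected in 9% of runs over all participants. Among attenders only it rejected in 37%, but that is a post-randomization subset which the plan does not specify for H1.3.

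**The case against.** The strongest reply is that item L sits in an assessment list common to both arms, that assessments may be done by telephone, and that Table 1 schedules adherence at the common visits. The telephone calls could then be the assessment calls. That reading is open, and no sentence says that coaching calls will count sessions. But item L does not exclude them, and they are the only recurring participant calls described. The point stands as something the plan permits.

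Onsite program data are listed without restriction by arm, so site-based sessions could be counted equally in both. That also stands, and it narrows the exposure mainly to home-based and hybrid sessions.

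Several stronger readings are tempting, but the documents do not support them:

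- **SOC counts rest on recall at study end.** Program data and the scheduled visits are also available for SOC.
- **Home and hybrid sessions leave no record.** Hybrid CR begins on site, and home-based CR for MACRO includes at least weekly contact by qualified personnel (section 7.2), so program records may exist. Onsite data may merely not cover everything.
- **The bias must favor MACRO.** Late self-report can overstate as well as understate attendance.
- **Falls and adverse events are distorted by the same route.** Falls are already asked about at follow-up assessments (section 7.2, item G), and nothing in the text shows that coaching calls are a source of adverse-event counts.

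**Conclusion.** The concern holds in limited form. As written, the plan allows the H1.3 session count to be ascertained differently by arm, with an unblinded, adherence-promoting source available only in MACRO, and nothing in the analysis plan corrects for it. Inflation in MACRO is the more plausible consequence, but neither direction nor size can be derived from the documents. The 11.4 vs 9.0 example and the false-positive rates rest on assumed capture rates and equal true attendance.

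Two features moderate the size. The Wilcoxon test on all participants is less sensitive to a capture gap (9% in the simulation) than the yes/no comparison (26% at the same rates). And missing every session of an attender should be less common than missing some, so the capture gaps in the yes/no table may be harsh.

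H1.3 is secondary, and the primary outcome and its sample size are untouched. The change should still be made, because it is cheap and measurement that differed by arm cannot readily be repaired afterwards.

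**What to change.** - **Source.** In section 7.2, item L, define the H1.3 count from sources identical in both arms: CR program attendance records (site or home), plus one standard question asked by the blinded assessor at the common follow-up visits. State which prevails when they disagree, and record the source of each count.
- **Coaching calls.** Exclude their logs from the outcome and report them only as intervention fidelity.
- **Sensitivity analysis.** Repeat the H1.3 comparison on program-recorded sessions only.
- **Timing.** Reconcile item L, Table 1 and the Aim 1 analysis so that one schedule applies, and make it consistent with H2.1.

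The cost is a change of wording, one case-report-form rule and one extra analysis, plus the work of obtaining program records in both arms. The downside is that some MACRO home sessions known only to coaches will not be counted, so a true MACRO advantage could be somewhat understated.

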## MACRO Intervention

**Early Contact.** MACRO study staff will continue to monitor inpatient participants electronic medical record charts for consults to PT/OT/CR. Education will be provided over the phone or in person to enhance the transition to home and to facilitate transition to outpatient CR. The rationale for CR will be explained and the shared decision making between the patient and providers will be emphasized.

**Risk Determination.** Aggregate risk assessment will be completed on each participant (both MACRO intervention and controls) with methods that integrate baseline study indices across three domains: medical, functional, and psychosocial. In the MACRO Intervention group only, these risk assessment scores will be used as a means to inform coaches of broad patient challenges that need to be addressed with CR care, as parts of site-, hybrid- and home-based options.

**MACRO Intervention arm transitional care:** The MACRO Intervention includes therapeutic reinforcements in the days after discharge/enrollment. When feasible, home calls start the week of discharge/enrollment, study staff will contact the participant approximately once each week (intent to treat) to address questions and to encourage the patient to continue the chosen CR option (site-, home-, or hybrid). Phone calls will continue throughout the phase II CR period to help ensure adherence and as recovery evolves.

Our methods for maintaining care and observation throughout transitions (including to skilled term nursing facility [SNFs] or rehab) were developed at the VAPHS and include (1) Establishing rapport with potential participants and their families; (2) Collecting information for several different methods of contact to ensure close communication over the duration of the study; (3) Phone calls with participants intermittently while they are at SNF or inpatient rehab; (4) sending reminders to the participants and their family members that the team will be calling them; (5) Verification of discharge plan at SNF/rehab discharge and confirmation that alternate contact information is up-to-date.

**Patients in the MACRO Intervention arm will be encouraged to participate in outpatient phase 2 Clinical CR (site-, home- or hybrid-based options)**

**Site-based Clinical CR:** MACRO Intervention participants may be enrolled in outpatient site-based CR. In addition to the commitments and benefits of that program, participants will also receive weekly MACRO phone calls that reinforce complementary MACRO-based priorities. The emphasis of the calls is to

reinforce the site-based programs, and to also better facilitate the goal of transitioning from site-based CR to management the participant can achieve independently at home..

**Home-based Clinical CR:** MACRO Intervention participants may be enrolled in home-based CR. While home-based CR will vary with each site's clinical program and even within each program over time, minimal standards of home-based CR for MACRO will include at least weekly contact by qualified personnel, with implementation of a curriculum that offers requisite components of exercise training, education, support, and linkage to dietary consultation when indicated.

In addition to the commitments and benefits of the home-based program, participants in the MACRO intervention arm will also receive weekly MACRO phone calls that reinforce complementary MACRO-based priorities. The emphasis of the calls is to reinforce the home-based programs.

**Hybrid-based Clinical CR:** MACRO Intervention patients may also be enrolled in hybrid-based CR. Hybrid CR starts with site-based care, but then transitions to home-based care as the patient and clinicians feel suitable. The transition may be triggered by evolving medical stability, growing self-confidence, or other factors which impact on each patient's capacity for home-based CR. The time required for this transition will vary between individuals.

In addition to the commitments and benefits of the hybrid program, participants in the MACRO intervention arm will also receive weekly MACRO phone calls that reinforce complementary MACRO-based priorities. The emphasis of the calls is to reinforce hybrid CR.

**Responding to patients' goals and needs:** The MACRO Intervention arm tailors care to each participant in two ways, matching care to (1) the participant's personal preferences as part of Enhanced Medical Rehabilitation (EMR) goal setting and motivational; and (2) elements of risk that are detected as part of their comprehensive risk profile (that includes medical, physical, and psychosocial domains). The underlying premise is that each patient requires a personalized approach to integrate preferences and risks. MACRO's flexibility is an essential aspect of this management. The MACRO intervention, for example, emphasizes seated activities for patients with risks of falls. The MACRO intervention also organizes family supports, repetitive learning strategies, and community activity resources for participants with learning impairments. The MACRO intervention emphasizes strength, balance, and nutrition for participants who are frail.

